9.4.1.2. Intercurrent Event Strategies

Discontinuation of study intervention, as specified in Section 7.1, will be considered as intercurrent events.

For the primary and key secondary estimands, the following 2 types of intercurrent events will be considered:

- Discontinuation of treatment due to an AE, for lack of efficacy, or any other reason. Participants who experience this type of intercurrent event will be treated as if they did not experience an intercurrent event (hypothetical strategy). The hypothetical strategy used is defined as the pharmacologic effect of JZP385 compared to placebo assuming the intercurrent event did not happen with continuation of study intervention for the duration of the study. Analyses will be conducted using data collected at time points obtained at or prior to participants' discontinuation of study intervention and combined with imputed values for post-discontinuation time points for which the underlying assumptions are considered appropriate.
- Any change to concomitant antitremor medication use after the initiation of study intervention, including but not limited to the following: 1) starting a new antitremor medication, 2) stopping a concomitant antitremor medication, and 3) a dose or regimen change to current antitremor medication. This type of intercurrent event will be disregarded, and measurements obtained subsequently will be reported and analyzed (treatment policy). Treatment policy is defined as the effect of randomized treatment over the study period regardless of the occurrence of the intercurrent event. In accordance with treatment policy, data collected after this type of intercurrent event will be reported and included in analyses.

If a participant experiences a combination of both types of ICE (eg, change the use of anti-tremor medication and discontinue the study intervention afterwards), each ICE should be treated

independently. Data collected after the change of antitremor medication but on or before the study intervention discontinuation will be included in analyses per treatment policy, the postdiscontinuation data will be handled by hypothetical strategy.

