4.2. Study Estimands and Endpoints

4.2.1. Primary Estimand

The primary estimand of the study is defined as:

- Treatment: 10, 20, and 30 mg/day JZP385 and placebo.
- Population: Adults with moderate to severe ET.
- Variable: Change from Baseline to Week 12 on the TETRAS composite outcome score*.
- Intercurrent events:
 - o Discontinuation of treatment due to an AE, for lack of efficacy, or any other reason. Participants who experience any intercurrent event will be included as if they did not experience the intercurrent event (hypothetical strategy).

- O Any change to concomitant anti-tremor medication use after the initiation of study intervention, including but not limited to the following: 1) starting a new antitremor medication, 2) stopping a concomitant antitremor medication, and 3) a dose or regimen change to current antitremor medication. This type of intercurrent event will be disregarded, and measurements obtained subsequently will be reported and analyzed (treatment policy).⁺
- Summary: Difference in the mean TETRAS composite outcome score from Baseline to Week 12 between each dose of JZP385 and placebo.
- * The TETRAS composite outcome score is the sum of modified items 1 to 11 of the TETRAS-ADL subscale and modified items 6 and 7 of the TETRAS-PS. For TETRAS-ADL, each item is modified from 5 response items to 4 response items by collapsing options 0 and 1 together and for TETRAS-PS, each item is modified from 9 response items (due to 0.5 scoring increments) to 4 response items. As such, the range of possible scores at each visit is 0 to 42.
- + A blinded review of all concomitant medications and therapies will be performed prior to database lock to determine the occurrence of this intercurrent event.

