7.2.2. Study Day

A study day will be assigned as follows:

- The first dose of study intervention is designated as Day 1. Participants self-administer the first dose study intervention at home the day after the Baseline Visit.
- For visit days after Day 1, study day = visit date Day 1 date + 1.
- For visit days prior to Day 1, study day = visit date Day 1 date. Thus, study days for screening visit are negative numbers. There is no "Day 0".
- The end date of treatment for each subject is the subject's last dose date in the study.
- The end date of the study for each subject is defined as the date of the subject's last assessment including the safety follow-up in the study.

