7.2.3. Visit Windows

All scheduled, unscheduled, and early termination assessments will be summarized by derived analysis visit per the Table 5, regardless of whether the visit was performed on-site or remotely. Visit dates will be mapped based on the scheduled Period of each visit, with adjusted analysis-defined visit windows as specified in Table 5.

Table 5 Visit Windows for Assessments or Measurements

Study Period	Scheduled Visit	Scheduled Study Day	TETRAS-ADL, TETRAS-PS, CGIs	CGIc and PGIc	QUEST, SF-36v2, ETEA	C-SSRS ^b , Clinical Laboratory ^{c, e} , Urinalysis ^e , Weight, Vital Signs, Breath Alcohol ^{d, e} , ECG, Urine Pregnancy test
Screening	Visit 1/Visit 2 ^a	-49 to -8	Any Day up to -2	na	n/a	Any Day up to -2
Baseline ^f	Baseline Visit	-1	Closest prior to dosing	na	Closest prior to dosing	Closest prior to dosing
	Week 1	7 (-1, +2)	na	na	na	2 - 14
Double-Blind	Week 4	28±3	2 - 42	2 - 42	na	15 - 42
Treatment	Week 8	56± 3	43 - 70	43 - 70	na	43 - 70
	Week 12	84± 3	71 - 98	71 – 98	2 - max	71 - max
Safety Follow-up	End of Study	98± 3	na	na	2 - max	2 – max ^f

^a Screening Visit 2 is only for participants who need to wash out of any medications that impact tremor (e.g., anti-tremor medications) prior to Baseline;

^b At screening visit 1, C-SSRS screening/baseline version, at screening visit 2, C-SSRS since last visit version;

^c Clinical laboratory includes hematology and chemistry labs;

^dBreath Alcohol is not collected at W1;

^e Not collected at Safety Follow-up.

^f For participants who randomized without taking the study intervention, the Baseline Visit or latest Screening Visit (if Baseline Visit is not available) will be mapped.

If multiple assessments or measurements are recorded within a single visit window (including scheduled, unscheduled, repeated, and retest assessments or measurements as well as early discontinuation data), the following rules will be applied to determine the result from which assessment will be used for the summaries for that analysis visit.

- The priority will always be given to the scheduled visit within the corresponding visit window (e.g., scheduled W4 visit corresponds to Week 4 visit window) regardless of the relative distance to the scheduled Visit Day.
- If there are 2 or more observations within the same visit window, then the non-missing one closest to the scheduled Visit Day will be used in the analysis.

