7.6. Changes to Planned Analyses

Section 9.4.1.4 of the Protocol outlines the approach to imputation of missing item scores, as part of the TETRAS composite outcome score. Based on these rules, it was possible for a participant to have a missing TETRAS PS score at a visit and still have a valid composite outcome score. The rules have been amended to change the imputation of missing item scores to be managed within the individual subscale scores (ADL or PS) before the composite outcome score is calculated. The details of the new calculation are specified in Section 7.2.5.

The mITT Analysis Set defined in the Protocol Section 9.3 has been updated to ITT, to include all randomized participants for the primary efficacy analyses.

For Adverse Events of Special Interests defined in Protocol Section 8.4.6, presyncope was removed in the formal definition of AEOSI in Section 10.2.1.

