9.1.2. Primary Analyses

For the main analysis of the primary efficacy endpoint, a MMRM will be used to include the change in the TETRAS composite outcome score from Baseline to Weeks 4, 8, and 12.

$$dTCOM_{ij} = \alpha_i + \beta_1 * baseTCOM_i + \beta_2 * week_j + \beta_3 * treatment_i + \beta_4 * treatment_i * week_j + \beta_5 * baseTCOM_i * week_i + \beta_6 * stratum_i + \varepsilon_{ij}$$

The model will include treatment group ($treatment_i$), baseline TETRAS composite outcome score ($baseTCOM_i$), week (as a discrete factor, $week_j$), treatment group by week interaction ($treatment_k * week_j$), week by baseline interaction ($week_j * baseTCOM_i$), and randomization

stratum ($stratum_i$) as fixed effects, and week repeated within each participant as a repeated effect (α_i). For the purposes of this model, "week" refers to the treatment visit, as determined using the windows specified in Section 7.2.3. An unstructured variance-covariance matrix will be used to model the correlation among repeated measurements. If the model fails to converge on the Newton-Raphson Algorithm, the alternative Fisher scoring algorithm should be explored before considering other variance-covariance structures. Kenward-Roger's degrees of freedom will be used.

Least squares mean and standard error for Week 12 will be provided for each treatment group. The difference between the LS means of JZP385 and placebo for Week 12, along with the SE of the difference, 95% CI and associated p-value corresponding to testing the hypothesis of no difference between the treatment groups will also be provided.

The assumption of normality will be examined by obtaining a histogram and a QQ-plot on studentized residuals. Based on these plots, if there exists evidence to suggest the departure from the normality assumption, a non-parametric MMRM with the covariate and response variables replaced by their ranks will be used for the primary analysis.

The following is an example of SAS code for linear mixed model analysis:

PROC MIXED;

CLASS PATIENT TRT WEEK STRATUM;

MODEL CHG = BASELINE TRT WEEK STRATUM TRT*WEEK BASELINE*WEEK /

RESIDUAL OUTP=RESIDUAL DDFM=KR;

REPEATED WEEK/TYPE=UN SUB=PATIENT;

LSMEANS TRT*WEEK / CL DIFF ALPHA=0.05;

RUN;

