9.1.3. Sensitivity Analyses

Sensitivity analyses for the primary estimand will be conducted under the hypothetical strategy framework using the ITT Analysis Set. These sensitivity analyses will only be needed where the JZP385 group demonstrates a statistically significant improvement over the placebo group, based on the criteria outlined in Section 7.3.

[figure not shown]
Under the hypothetical strategy, the MAR assumption is being followed for the primary analysis, which supports the justification for using an MMRM model. This is supplemented by the possibility of data being MNAR, assessed under the sensitivity and supplemental analyses.

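### The SAP's visit windows do not put the protocol's discontinuation cut-off into operation, so early-discontinuation TETRAS values taken well after the last dose can enter the primary MMRM as observed

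*SAP*

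**What the plan says.** **Protocol**
- Section 9.4.1.2, on discontinuation under the hypothetical strategy: "Analyses will be conducted using data collected at time points obtained at or prior to" discontinuation of study intervention, combined with imputed values afterwards. For a participant with both types of intercurrent event it repeats the limit: "Data collected after the change of antitremor medication but on or before the study intervention discontinuation will be included in analyses per treatment policy".
- Section 7 allows for an E/D visit two or more weeks after the last dose, in which case no further safety visit is needed. The Schedule of Activities (SoA) places TETRAS-ADL, TETRAS-PS and CGI-S at the E/D visit.
- Section 7.1 says that a participant who permanently stops study intervention does not stay in the study.

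**SAP**
- Section 7.2.3: "All scheduled, unscheduled, and early termination assessments will be summarized by derived analysis visit per the Table 5". For TETRAS and CGI-S, Days 2-42 are Week 4, Days 43-70 are Week 8 and Days 71-98 are Week 12. Early-discontinuation data are named in the selection rules. A scheduled visit has priority in its window, and a visit is missing only if its window holds no observation.
- Section 9.1.2: week in the primary MMRM "refers to the treatment visit, as determined using the windows specified in Section 7.2.3".
- Section 7.2.2: "The end date of treatment for each subject is the subject's last dose date in the study". No efficacy section uses this date to select data.
- Section 9.1.3 keeps the hypothetical label: "Sensitivity analyses for the primary estimand will be conducted under the hypothetical strategy framework using the ITT Analysis Set".
- Section 7.6 lists three changes: item imputation, the analysis set ("The mITT Analysis Set defined in the Protocol Section 9.3 has been updated to ITT") and the adverse-event-of-special-interest definition. The discontinuation cut-off is not among them.

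**The concern.** The protocol says which data count. The SAP rules that a programmer would follow for the primary model do not apply that limit. An E/D value taken well after the last dose falls in a window, makes that visit non-missing, and is then not handled as missing by the MMRM or by multiple imputation.

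The primary estimate could then mix on-drug and off-drug values and no longer match the stated estimand. The model is also the first gate in the testing hierarchy (SAP 7.4). The choice of which E/D values qualify would be left to programming.

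SAP 4.2.1 and 4.2.2 add to the uncertainty. They omit the protocol's combined-event rule and say that measurements after an antitremor change are analysed. They do not address a participant who stops study drug, changes antitremor medication, and then attends a delayed E/D visit.

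**Working it through.** **1. The plan's own figures.** Inputs from Protocol 9.2 and SAP 5.3: difference 3.1, SD 6.0, 80 evaluable per arm, 2-sided 0.05, 20% dropout.
- TETRAS: noncentrality = 3.1 / (6.0 × √(2/80)) = 3.1 / 0.949 = 3.27, so t-test power is 90.1% (stated 90%).
- CGI-S, 66% vs 40%: z = (0.26 × √80 − 1.96 × √(2 × 0.53 × 0.47)) / √(0.40 × 0.60 + 0.66 × 0.34) = (2.326 − 1.383) / 0.681 = 1.38, so power is 91.7% (as stated).
- 80 / 0.80 = 100 per arm, × 4 = 400.

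**2. One participant traced.** Last dose Day 57, E/D visit Day 71. Day 71 lies in 71-98, so the value becomes an observed Week 12 score 14 days off drug. Under Protocol 7.1 no scheduled Week 12 visit will displace it. With Week 4 and Week 8 scores, the participant is also a completer under SAP 9.1.4.

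**3. How many reach Week 12.** Assume last dose uniform on Days 2-83 (82 days) and an off-drug E/D visit 2-14 days later (13 delays): 82 × 13 = 1066 pairs. For delay L, 13 + L last-dose days land in 71-98. Summed over L = 2 to 14 this is 169 + 104 = 273, or 25.6%. With 20 dropouts per 100, that is 20 × 0.256 = 5.1 per 100 if all E/D visits are off drug and 2.6 if half are. Leaving out last doses on Days 81-83, which lie inside the scheduled Week 12 visit window, gives 234/1027 = 22.8%, or 2.3 per 100 if half are. If 60% of dropouts stop by Day 28, the figures are 3.1 (all) and 1.5 (half).

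**4. Direct Week 12 route in closed form.** Let a share s of the 20 dropouts have an off-drug value in that window, with full loss of effect. The difference is 3.1 × 80 / (80 + 20s).
- s = 0.25: 3.1 × 80/85 = 2.92, power 88.1%.
- s = 0.50: 3.1 × 80/90 = 2.76, power 86.1%.
- s = 1: 2.48, power 82.1%.

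For CGI-S, the same shares turn 26.0 points into 24.5, 23.1 and 20.8, with power 89.8%, 88.0% and 84.2%.

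**5. All windows, by simulation.** Off-drug values at Weeks 4 and 8 also pull the Week 12 estimate through the correlations. Assumptions, none of them from the documents: 100 per arm, 20%/20% dropout, SD 5/5.5/6, correlations 0.70 (W4-W8), 0.65 (W4-W12) and 0.75 (W8-W12), uniform or early dropout, and a flat or rising effect that reaches −3.1 at Week 12. Estimation was by maximum likelihood under missing at random, with 6000 replicates per scenario. Dilution = 1 − |estimate| / 3.1.

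| E/D visits off drug | Effect kept off drug | Estimate as mapped | Dilution |
|---|---|---|---|
| half, 70% attendance | half | −3.02 to −3.05 | 1.6-2.6% |
| half | half | −2.98 to −3.02 | 2.6-3.9% |
| half | none | −2.87 to −2.93 | 5.5-7.4% |
| all | half | −2.86 to −2.91 | 6.1-7.7% |
| all | none | −2.64 to −2.76 | 11.0-14.8% |

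With off-drug values removed, the estimate is −3.08 to −3.11. Power falls from about 91-93% to 89-91% in the third and fourth rows, and from about 92-93% to 84-87% in the last. A second simulation (SD 6 throughout, correlation 0.5 or 0.7, every dropout off drug with full loss, E/D visit 1, 7 or 14 days after the last dose) gave differences of 2.81, 2.72 and 2.69-2.70, against 3.09-3.10 with exclusion.

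**6. Direction.** True effect zero, half of E/D visits off drug, and an assumed 3-point benefit from resumed antitremor medication. With 20%/20% dropout the bias is zero. With 30% on JZP385 and 10% on placebo, a rough ceiling is (0.30 − 0.10) × 0.5 × 3 = 0.30 points. The model gives −0.24, in favour of JZP385, and −0.12 if only half resume. With 10% and 30% it is +0.24, against JZP385.

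**7. Sensitivity analyses.** The control-based step (SAP 9.1.3.1) resets only imputed values, the tipping point (9.1.3.2) worsens only imputed values, and non-responder imputation (9.2.3) acts only on missing data. None of them touches an observed off-drug value.

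**The case against.** The strongest reply is that the SAP is silent, not contradictory. It is based on Amendment 04, keeps the hypothetical strategy, and lists its changes without touching Protocol 9.4.1.2. Several passages suggest that values after discontinuation were meant to be imputed:
- SAP 9.1.3.1 works from observed values before withdrawal and speaks of imputed post-discontinuation values.
- SAP 9.2.2 sends treatment dropouts to multiple imputation.
- SAP 9.2.6.3 and 9.2.6.4 exempt QUEST and ETEA from imputation after intercurrent events, which makes most sense if other endpoints are not exempt.

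Many E/D values may also be legitimate. Protocol 7.2 places the visit at the time of discontinuing, and Protocol Table 5 labels the E/D TETRAS-PS 1-hour postdose. Remote E/D visits yield no TETRAS-PS and so no composite. Scheduled visits take priority.

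All of this stands as evidence of intent and as a limit on numbers. It does not close the gap, because none of these passages governs the primary model. Sections 7.2.3 and 9.1.2 do, and they admit the values.

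Stronger readings are tempting but not supported:
- A reader might infer that the SAP chose to analyse off-drug data. It nowhere says so.
- A reader might infer that late E/D visits are common. Protocol Section 7 only provides for the case and gives no frequency.
- A reader might infer a bias in favour of JZP385. That needs markedly unequal dropout and a resumed-medication benefit about as large as the planned drug effect. Inclusion Criterion 7 keeps permitted antitremor drugs stable, so mainly participants washed out of a prohibited drug have something to resume. Protocol 6.6 speaks of resumption after the study ends.
- A reader might infer that the protocol demands a strict last-dose-date cut. It says discontinuation, and a strict cut would delete next-day E/D values.

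**Conclusion.** The concern holds as a gap in operation: the protocol's cut-off is not carried into the SAP rules that build the primary analysis dataset. Only E/D values collected after discontinuation, in a window without a scheduled visit, are affected. CGI-S shares the Table 5 column, but the case there is weaker.

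Size depends on E/D timing, attendance and persistence of effect, none of which the documents give. With 20%/20% dropout and no resumed medication, the dilution is about 3-8% in moderate cases. It reaches about 15% only if every dropout is assessed off drug with full loss of effect. Dilution is the likelier direction, but it is not assured once dropout differs between arms and antitremor medication is resumed; the 0.24-point figure shows that possibility and is not a forecast. This should be fixed: the effect is modest in most settings, but it falls on the primary estimand and the remedy is cheap.

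**What to change.** Before unblinding:
- State in SAP 7.2.3, 9.1.2 and 9.2.2 that, for the primary and key secondary estimands, TETRAS composite and CGI-S values collected after discontinuation of study intervention are set to missing before window mapping and then handled by the MMRM or multiple imputation.
- Define at discontinuation by a prespecified interval from the last-dose date in SAP 7.2.2, so that E/D values taken at discontinuation are kept. List this in SAP 7.6 as a clarification of Protocol 9.4.1.2.
- Carry the combined-event rule into SAP 4.2.1 and 4.2.2.
- Apply the same flag in the control-based, tipping-point, non-responder and completers analyses.
- Reconcile Protocol Table 5, which labels the E/D TETRAS-PS 1-hour postdose, with the SoA, which marks no on-site dosing at E/D.

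An as-mapped supplementary analysis is optional.

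Cost: a few sentences and one derived flag. Under the assumptions above, about 8-9 observed values per 100 randomized are lost if half of E/D visits are off drug (Week 12 standard error about 2% larger), and 17-18 per 100 if all are (about 3.5% larger). An interval that keeps some of these visits lowers the loss. The sponsor has to choose that interval without knowledge of treatment.

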- ^d If participant discontinues study intervention and requires an E/D Visit, the Safety FU should be 2 weeks after the E/D visit.
- ^e Clinic visits at Week 1, Week 4, Week 8, E/D, and EoS/Safety FU may be conducted remotely, if required due to the COVID-19 pandemic, and with approval from the sponsor's medical monitor. The TETRAS-PS will not be performed at remote visits, and PK samples may not be collected.
- f Phone contacts at Weeks 2 to 3, Weeks 5 to 7 and Weeks 9 to 11 may be converted to clinic visits if required due to local regulations or local requirements. If performed in-clinic, dispensing of study intervention may occur and urine pregnancy testing should be completed for WOCBP.

CONFIDENTIAL Page 26 of 109

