7. DISCONTINUATION OF STUDY INTERVENTION AND PARTICIPANT DISCONTINUATION/WITHDRAWAL

Discontinuation from study intervention does not represent withdrawal from the study (Section 7.2). Participants may discontinue from study intervention at any time for any reason, or at the discretion of the investigator. In addition, a participant may be dropped from study intervention by the investigator or sponsor for safety, behavioral, compliance and/or administrative reasons.

For participants who discontinue study intervention, all effort should be made to complete the procedures listed in the Early Discontinuation Visit (Section 1.3). Participants should be asked to return 2 weeks later for the EoS/Safety Follow-up Visit. If the Early Discontinuation Visit occurs 2 or more weeks after the last dose of study intervention, an additional safety follow-up visit is not required.

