10.2. Adverse Events

Adverse events (AEs) occurring from the first dose until the final study visit will be reported. If the Investigator becomes aware of a SAE within 14 days after the last dose of study intervention, the event must also be reported. In addition, any SAE assessed as related to study intervention or procedure by the Investigator must be reported regardless of time after study termination.

AEs will be coded to system organ class (SOC) and preferred term using the Medical Dictionary for Regulatory Activities (MedDRA), Version 27.0. The investigator will assess the relationship of each AE to study intervention. AE with a missing relationship to study intervention will be reported as related in the summaries. Severity, as determined by the Investigator, will be classed as mild, moderate, severe, life-threatening or fatal. AE with missing severity will be reported as missing in the summaries.

Note that participants who acquire COVID-19 or report AEs due to the COVID-19 public health emergency (e.g., anxiety) while on study will be coded accordingly and included in the adverse event summaries.

A treatment-emergent adverse event (TEAE) is defined as any event with onset date on or after the first dose of study intervention, including adverse events that occur until 14 days after the last dose date. For the purpose of calculating treatment emergence, incomplete onset dates will be imputed as detailed in Appendix 1: Date Imputation Rules.

Time of first onset of AE is calculated as: TEAE start date – First dose date + 1 and is categorized as:

- Week 1 ($1 \le \text{day of first onset of AE} \le 7$)
- Week 2 ($8 \le \text{day of first onset of AE} \le 14$)
- Week 3 (15 \leq day of first onset of AE \leq 21)
- Week 4 ($22 \le \text{day of first onset of AE} \le 28$)
- Weeks 5 to 8 (29 \leq day of first onset of AE \leq 56)
- Weeks 9 to 12 (57 \leq day of first onset of AE \leq 84)
- After Week 12 (84 < day of first onset of AE)

Only TEAEs are included in summary tables unless otherwise specified. If a subject has multiple episodes of events coded to the same SOC or PT, then the subject will be counted just once in the summaries for that term. Subject incidence of TEAEs by SOC and PT tables are sorted by SOCs (alphabetical order) and then by PTs (descending order) within each SOC for the overall frequency. For summaries by PT only, PTs will be sorted in descending order of overall frequency.

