10.4. Vital Signs

The following vital signs measurements will be reported for this study.

- Supine and standing systolic blood pressure (SBP), (millimeter of mercury [mmHg])
- Supine and standing diastolic blood pressure (DBP) (mmHg)
- Supine and standing pulse rate (beats per minutes [bpm])
- Sitting or supine respiratory rate (breaths/min)
- Body Temperature (°C)
- Weight (kg)
- Height (cm)
- BMI (kg/m2) [derived]

The orthostatic vital signs will be derived as the difference found by subtracting the supine measurement from the standing measurements. The orthostatic measurement will be summarized with the supine and standard measurements.

These vital signs (with the exception of the BMI which will be calculated programmatically) will be measured during the screening visit and each in-clinic scheduled visit. Height (cm) will be obtained at screening visit only.

The following summaries will be provided for vital signs data:

Jazz Pharmaceuticals

Statistical Analysis Plan - Protocol JZP385-201

- Observed and change from baseline by visit
- Incidence of markedly abnormal criteria by visit

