10.5. ECG

A standard 12-Lead ECG will be recorded with the subject resting in supine for at least 5 minutes. ECGs will be performed during the Screening visit, Baseline visit, in-clinic scheduled visit or early termination visit. Results from the central ECG core lab will be included in the reporting of this study. The following ECG parameters will be reported:

- PR Interval (msec)
- RR Interval (msec)

Jazz Pharmaceuticals

Statistical Analysis Plan - Protocol JZP385-201

- QRS Interval (msec)
- QT Interval (msec)
- QT Bazett's correction (QTcB) Interval (msec) [derived]
- QT Fridericia's correction (QTcF) Interval (msec) [derived]
- Mean HR (bpm)
- Overall assessment of ECG:
 - Normal
 - o Abnormal

The following summaries will be provided for ECG data across the study:

- Observed and change from baseline by visit (for quantitative measurements)
- ECG parameters results will be listed over time

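### An Early Discontinuation Visit that replaces the Safety Follow-up Visit has its ECG and vital signs summarized under a treatment week, so off-drug values can enter on-treatment safety tables

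*SAP*

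**What the plan says.** - **Protocol 7** sets the substitution rule: "If the Early Discontinuation Visit occurs 2 or more weeks after the last dose of study intervention, an additional safety follow-up visit is not required". For that participant the E/D Visit is the last safety contact. In the ordinary case, per the footnotes to the Schedule of Activities (Protocol 1.3), "the Safety FU should be 2 weeks after the E/D visit".
- **SAP 7.2.3** puts E/D data through the visit windows: "All scheduled, unscheduled, and early termination assessments will be summarized by derived analysis visit per the Table 5". On how, it says "Visit dates will be mapped based on the scheduled Period of each visit", with the day limits of Table 5.
- **SAP Table 5**, safety column, gives Week 1 as Days 2-14, Week 4 as Days 15-42, Week 8 as Days 43-70 and Week 12 as Day 71 onward. End of Study, the only visit in the Safety Follow-up period, is open from Day 2 onward. There is no E/D row, and no rule uses the last-dose date.
- **Competing values in one window** (SAP 7.2.3): "The priority will always be given to the scheduled visit within the corresponding visit window". Otherwise the value closest to the scheduled day is used.
- **SAP 10.4** promises "Observed and change from baseline by visit" for vital signs, a list that includes weight. It also promises markedly abnormal values by visit. SAP 10.5 promises the same by-visit summary for ECG, and 10.5.1 classifies QT and QTc at each time point. None of these carries an on-drug restriction.
- **SAP 10.2** does use the last-dose date for adverse events. Treatment emergence runs from first dose, "including adverse events that occur until 14 days after the last dose date".

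**The concern.** The protocol treats a late E/D Visit as sufficient safety follow-up, while the SAP windows it as a treatment-period observation. An ECG or blood pressure taken two weeks or more after the last dose can then appear in a week row of the 10, 20 or 30 mg arm. On-site dosing is scheduled at Weeks 1, 4, 8 and 12 and not at E/D, so the other values in that row come from visits with a dose given in the clinic.

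At stake is the reading of the by-visit change-from-baseline and threshold tables. Safety is analyzed descriptively only, so these tables carry the comparison between arms. If early stopping rises with dose, the highest arm would hold most of the off-drug values, and any drug effect on blood pressure, pulse or QTc would be diluted most there. The End of Study row should show values after stopping, and it may lack people for whom the E/D Visit was the follow-up.

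**Working it through.** There is no stated figure to reproduce; the check is on the window logic.

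**1. Which row does the visit fall in?** The week windows 2-14, 15-42, 43-70 and 71 onward leave no day uncovered from Day 2. The earliest possible substitute visit is last dose Day 1 + 14 = Day 15, so Week 1 is never reached and the row is Week 4, 8 or 12.

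| Last dose | E/D Visit | Days since last dose | Row |
|---|---|---|---|
| Day 5 | Day 19 | 14 | Week 4 |
| Day 20 | Day 35 | 15 | Week 4 |
| Day 30 | Day 46 | 16 | Week 8 |
| Day 60 | Day 75 | 15 | Week 12 |

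In the third case treatment emergence ends on Day 30 + 14 = Day 44. An adverse event starting on Day 46 is not treatment-emergent, while that day's ECG is summarized as Week 8.

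**2. Does a scheduled visit displace it?** Protocol 7.1 says a participant who permanently stops does not remain in the study, so only a scheduled visit already attended can hold the window. Take last-dose days 1 to 83, with E/D exactly 14 days later.

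- Scheduled visits on the nominal day: the window is held only for last dose on Day 28 (E/D Day 42) or Day 56 (E/D Day 70). The E/D value stands alone in 81/83 = 97.6% of cases.
- Scheduled visits 3 days early (Days 25, 53, 81): the window is held for last doses on Days 25-28, 53-56 and 81-83, which is 4 + 4 + 3 = 11. The E/D value stands alone in 72/83 = 86.7%.
- Gaps of 14 to 28 days (upper limit assumed): 1,243/1,245 = 99.8% on nominal days and 1,180/1,245 = 94.8% with visits 3 days early.

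These are shares of possible last-dose days and gaps, not of participants.

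**3. How many participants?** Planned dropout is 20% of 100, or 20 per arm. The share with a late E/D Visit is not given.

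- Assumed 10% to 30%: 2 to 6 per arm.
- Assumed 5% to 50%: 1 to 10 per arm, or 4 to 40 of the 80 planned dropouts overall.

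If 2 to 6 all fell in one window, they would be 2/100 = 2% to 6/(80 + 6) = 7.0% of that row; spread over three windows, less.

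**4. How far off drug?** Protocol 4.3 gives steady state in 5 days. If that is 4 to 5 half-lives (assumption), the half-life is 1 to 1.25 days and 14 days is 11.2 to 14 half-lives. At most 2^-11.2 = 0.04% of parent drug remains. Protocol 2.2 names two active metabolites and gives no half-life for them, so this covers the parent drug only.

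**5. Is the End of Study row affected?** Table 5 assigns no period to E/D. The Schedule of Activities shows E/D as a separate column before EoS/Safety FU, and the Safety Follow-up heading appears to cover EoS only. On that reading the visit belongs to treatment and End of Study omits the participant, while an early stopper with a separate follow-up visit is filed there. On a date-only reading, the Day 2 onward window also admits the visit, and it could sit in both rows. The week row receives the value on either reading.

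**The case against.** **C-SSRS.** A reader might infer that the C-SSRS result is misfiled in the same way. It is not. After screening the Since Last Visit version is used, so the result covers an interval. With last dose on Day 54, E/D on Day 68 and the last clinic visit on Day 28, the look-back contains Days 29-54, or 26 dosing days. Moving it to End of Study would take on-drug information out of the treatment rows. This objection stands in full.

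**Loss from End of Study.** A reader might also take this as certain. It rests on an inferred period for the E/D Visit, so it can be stated only conditionally.

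**Row labels.** Table 5 names weeks, not exposure, and the SAP promises summaries by visit, so nothing is expressly labelled on-drug. But the rows sit under Double-Blind Treatment and are tabulated by dose arm, and that is how they will be read.

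**The 14-day cut.** On the same half-life, an E/D Visit 7 days after last dose is 5.6 to 7 half-lives out (about 2% to 1% of parent drug left) and would still sit in a week row. A visit exactly 14 days out is follow-up under Protocol 7, while an adverse event that day is still treatment-emergent. Both observations are correct. The case for a change is that equivalent follow-up visits should share a row, not that the week rows can be cleared of every off-drug value. Weight also changes slowly, so the washout argument is weaker for it.

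**Consequence.** The substitute visit is the exception to the protocol's usual sequence, and some of the 20 dropouts per arm will attend no E/D Visit at all. Listings keep the nominal visit, and markedly abnormal ECGs are listed by participant, so the results can be traced. This limits the importance but does not remove the misfiling.

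**Conclusion.** The point holds for ECG and vital signs, including weight. As written, SAP 7.2.3 files a substitute E/D Visit under Week 4, 8 or 12 by study day unless a scheduled visit already holds the window, in which case the E/D value does not enter the week row. Omission from End of Study follows only on the period-based reading.

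The size is small and not known from the documents: probably a few participants per arm, resting on an assumed share of the planned dropouts. A reader might infer a demonstrated dilution of dose-related effects. The documents do not support that, because they give neither the number of late E/D Visits nor their split by arm. Nor do they show that these values are free of all drug effect, since the metabolites' half-lives are not given. The effect is confined to descriptive by-visit safety tables; the efficacy analyses are not part of this point. It is a worthwhile, low-priority correction.

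**What to change.** Add to SAP 7.2.3: ECG and vital signs (including weight) from an E/D Visit that replaces the Safety Follow-up Visit under Protocol 7 are mapped to End of Study and not to a treatment week. The End of Study window is already open from Day 2, so no limit in Table 5 changes. An emptied week window stays missing, as SAP 7.2.3 already provides.

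Leave C-SSRS in its by-day row. Laboratory results are collected at E/D but have no follow-up row. They need no new one; flag them as taken 14 or more days after last dose.

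The cost is a short addition to the text, one derivation from the last-dose date (already defined in SAP 7.2.2) and the laboratory flag. The downside is slightly fewer values in some week rows.
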